Children's Depression Rating Scale-Revised (CDRS-R)	X	X	X	X	X	X	X	X	X	X	X	X	X		
Pediatric Anxiety Ratings Scale (PARS)	X	X	X	X	X	X	X	X	X	X	X	X	X		
Adverse Events	X	X	X	X	X	X	X	X	X	X	X	X	X	X	X
Concomitant Medications	X	X	X	X	X	X	X	X	X	X	X	X	X	X	
Dispense Study Drug	X	X	X	X	X	X	X	X	X	X	X	X	X^3		
Collect Unused Study Drug/Assess Drug Compliance		X	X	X	X	X	X	X	X	X	X	X	X	X	

Confidential

Abbreviations: BP = blood pressure, CGI = Clinician Global Impression, CGI-TS-I = CGI Tourette Syndrome of Improvement, CGI-TS-S = CGI Tourette Syndrome of Severity, ECG = electrocardiogram, HbA1c = Hemoglobin A1c

^{*} Baseline is to occur within 30 days of the EBS-101-CL-001 14 Day Follow Up Visit (or longer with the permission of the medical monitor). All Baseline measurements can be taken from the Day 14 Follow Up Visit of the EBS-101-CL-001 study if performed less than 7 days prior to the Baseline visit. In this case, the HbA1c and Urine Drug Screen from the Week 12/Completion Visit of the EBS-101-CL-001 study may be used.

¹ Vital signs will include heart rate, BP, orthostatic BP and heart rate (done supine and then 3 minutes after standing), height and weight.

² Subjects should be in a fasting state (8 hours) for laboratory tests.

³ Study drug dispensation for down titration.

⁴ Assessments for Study Visits may be completed in locations other than study clinic and/or safety and efficacy assessments required at these visits will be made available for remote administration due to restrictions as a consequence of the COVID-19 pandemic or other qualifying event.

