12. ASSESSMENT OF SAFETY

12.1. Safety Parameters

Study Visits may be completed in locations other than clinic and/or via remote administration due to restrictions as a consequence of the COVID-19 pandemic or other qualifying event. Safety will be monitored throughout the study at all visits by repeated adverse event (AE) monitoring, vital signs, the Columbia-Suicide Severity Rating Scale (C-SSRS), the Abnormal Involuntary Movement Scale (AIMS), the Barnes Akathisia Rating Scale (BARS), the Pediatric Anxiety Rating Scale (PARS) and Children's Depression Rating Scale-Revised (CDRS-R). In addition to these assessments, at Baseline, Months 1, 3, 6, 9 and 12 safety will also be monitored by clinical and laboratory evaluations and electrocardiogram (ECG) monitoring. At the Follow Up visit, AE monitoring, the C-SSRS, clinical and laboratory evaluations and vital signs will be assessed. Laboratory evaluations will include hematology, chemistry, urine values and HbA1c. A Follow Up phone call will be conducted 30 days after the last dose of study medication to assess AEs. Additional assessments (all visits except the follow up visit) will include the AIMS, the BARS, the CDRS-R and the PARS. C-SSRS will also be assessed (all visits including the Follow Up visit).

The C-SSRS is a low burden (approximately 5 minutes for completion) instrument to assess both suicidal behavior and ideation. The scale is appropriate for subjects from age 6 through to an elderly population.

The AIMS records the occurrences of tardive dyskinesia (TD) in subjects receiving neuroleptic medications. The test is used to detect TD and to follow the severity over time.

Barnes Akathisia Rating Scale (BARS) scale to assess the severity of drug-induced akathisia. Objective and subjective items in the scale measure the level of subject's restlessness.

Children's Depression Rating Scale-Revised (CDRS-R) is a clinically validated rating scale designed to assess psychiatric signs and symptoms of depressions in children and adolescents.

Pediatric Anxiety Rating Scale (PARS) is a clinician-rated instrument for assessing the severity of anxiety symptoms associated with common anxiety disorders and generalized anxiety in children and adolescents.

Vital Signs:

Vital signs will be collected each clinic visit. They include heart rate, blood pressure, orthostatic blood pressure and heart rate (after being supine for 5 minutes and 3 minutes after standing), height and weight.

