9.5. Vital Signs

Vital sign measurements including sitting systolic blood pressure, sitting diastolic blood pressure, sitting pulse rate, supine orthostatic systolic blood pressure, supine orthostatic diastolic blood pressure, supine pulse rate, standing orthostatic systolic blood pressure, standing orthostatic diastolic blood pressure, and standing pulse rate at each scheduled time and changes from baseline in vital sign measurements will be summarized with descriptive statistics at each scheduled time point.

Body height will be measured at Baseline and will be summarized. Weight will be measured at each schedule visit and, along with changes from baseline, will be summarized with descriptive statistics at each scheduled time point. Weight will be displayed in kilograms; height will be displayed in centimeters.

Body mass index (BMI) will be derived from the weight at each visit and from height (at screening), along with changes from baseline, will be summarized with descriptive statistics at each schedule timepoint.

BMI will be displayed in kilograms per meter squared.

The Centers for Disease Control and Prevention (CDC) growth charts will be used to calculate weight z-score, height z-score and BMI z-scores. Shift (0.5 change ranging from <-3 to >3) from baseline will be summarized for weight z-score, height z-score and bmi-z score by visit. Mean BMI, height and weight z-scores over time will be illustrated in a figure.

Heart rate outliers such as >25% decrease change from baseline, <50, >25% decrease change from baseline and <50 as well as >25% increase change from baseline, >100, >25% increase change from baseline and >100 will be summarized by visit and overall.

All vital signs data will be presented in a listing.

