- Shifts from baseline summaries in BMI z-score, height z-score, and weight z-score will be generated and provided in Table 14.3.4.6a, Table 14.3.4.6b, and Table 14.3.4.6c, respectively. Mean BMI, height, and weight z-scores over time will be illustrated in Figure 14.3.4.6a, Figure 14.3.4.6b, and Figure 14.3.4.6c, respectively.
- A summary of shifts from baseline in 12-lead ECG QTc will be provided in Table 14.3.4.7a. A summary of outliers in 12-lead ECG will be provided in Table 14.3.4.7b.
- A summary of heart rate outliers will be provided in Table 14.3.4.7c.
- Shifts from baseline in HbA1c and total cholesterol will be provided in Table 14.3.4.8 and Table 14.3.4.9, respectively.

This document is confidential.

- Generation of listings for ITT Set: Listing 16.2.4.1b (demographics and baseline characteristics), Listing 16.2.6.1b (YGTSS), Listing 16.2.6.2b (CGI-TS), and Listing 16.2.6.3b (C&A-GTS-QOL).
- Generation of listings for Safety Set: Listing 16.2.9.1 (Height, Weight, and BMI z-scores).
- Generation of figures: mean changes from baseline for C&A-GTS-QOL total score (Figure 14.2.1.4.1a), mean changes from baseline for C&A-GTS-QOL VAS (Figure 14.2.1.4.1b), mean BMI, Height, Weight z-scores over time (Figures 14.3.4.6a, 14.3.4.6b and 14.3.4.6c).

This document is confidential.

11. Reference List

2. [SAS Program \(ages 0 to < 20 years \) | Resources | Growth Chart Training | Nutrition | DNPAO | CDC](#)

This document is confidential.

12. Programming Considerations

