	16.2.8.4	Physical Examination	Safety Set
	16.2.8.5.1	Columbia-Suicide Severity Rating Scale (C-SSRS) – Suicidal Ideation	Safety Set
	16.2.8.5.2	Columbia-Suicide Severity Rating Scale (C-SSRS) – Intensity of Ideation	Safety Set
	16.2.8.5.3	Columbia-Suicide Severity Rating Scale (C-SSRS) – Suicidal Behavior	Safety Set
	16.2.8.5.4	Columbia-Suicide Severity Rating Scale (C-SSRS) – Actual Attempts	Safety Set
	16.2.8.6	Abnormal Involuntary Movement Scale (AIMS)	Safety Set
	16.2.8.7	Barnes Akathisia Rating Scale (BARS)	Safety Set
	16.2.8.8	Children's Depression Rating Scale Revised (CDRS-R)	Safety Set
	16.2.8.9	Pediatric Anxiety Rating Scale (PARS)	Safety Set
	16.2.9.1	Height, Weight and BMI Z-Scores	Safety Set

This document is confidential.

16. Index of Figures

Header	Figure Number	Name	Analysis Set (Example)
14.2	14.2.1.4.1a	Mean (+/- SD) C&A-GTS-QOL Change from Baseline Total Score Over Time	miITT Set
	14.2.1.4.1b	Mean (+/- SD) VAS Change from Baseline Score Over Time	miITT Set
14.3	14.3.4.6a	Mean (+/- SD) BMI z-Score Over Time	Safety Set
	14.3.4.6b	Mean (+/- SD) Height z-Score Over Time	Safety Set
	14.3.4.6c	Mean (+/- SD) Weight z-Score Over Time	Safety Set

This document is confidential.

17. Appendices

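### SAP 9.5 divides each visit's weight by a fixed screening height, so the BMI change from baseline is biased upward in any child who grows and can have the wrong sign

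*SAP*

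**What the plan says.** SAP 9.5 has two sentences on height. On collection: "Body height will be measured at Baseline and will be summarized". On BMI: "Body mass index (BMI) will be derived from the weight at each visit and from height (at screening), along with changes from baseline", with descriptive statistics at each scheduled time point. Weight is handled differently: "Weight will be measured at each schedule visit and, along with changes from baseline, will be summarized with descriptive statistics".

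The protocol collects height throughout. Footnote 1 to Table 2 reads: "Vital signs will include heart rate, BP, orthostatic BP and heart rate (done supine and then 3 minutes after standing), height and weight". Table 2 marks vital signs at Baseline, at every monthly visit and at the follow-up visits, and Protocol 12.1 says: "Vital signs will be collected each clinic visit". Table 2 has no screening visit.

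SAP 9.5 then plans analyses that need later heights: "Shift (0.5 change ranging from <-3 to >3) from baseline will be summarized for weight z-score, height z-score and bmi-z score by visit". SAP 10 repeats this ("Shifts from baseline summaries in BMI z-score, height z-score, and weight z-score will be generated") among the items added after database lock, and SAP 16 lists a figure titled "Mean (+/- SD) Height z-Score Over Time". SAP 10 does not list a fixed-height BMI among the changes from the protocol. SAP 7.2 gives the ordinary BMI formula without saying which visit's height applies.

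**The concern.** BMI is reported alongside weight in order to separate gain in weight for height from growth. With a frozen denominator it cannot do that: a child's BMI change is then the weight change divided by a constant, and any weight gain appears as a BMI rise. A growing child whose BMI is truly constant shows an increase, and so can one whose BMI falls.

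This matters here because Protocol 13.2.1 places weight gain under a metabolic adverse event of special interest, and Protocol 5.3.1 reports that nearly all children in the earlier pediatric open-label extension gained weight. The useful question is whether such gain exceeds growth. Raw weight and fixed-height BMI are the only body-size measures with a planned numeric change from baseline, and both rise with normal growth.

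Two ambiguities add to the problem. Screening height is undefined in a study without a screening visit. The SAP also does not say which height feeds the BMI z-score. If it is the fixed height, the BMI z-score shifts and figure carry the same bias. If it is the visit height, the BMI table and the BMI z-score tables can contradict each other.

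**Working it through.** The plan states no BMI figure, so there is nothing to reproduce. The check is algebra followed by worked cases.

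**Inputs from the documents**
- BMI = weight (kg) / height (m) squared (SAP 7.2).
- Change = post-baseline value minus baseline value (SAP 6.2).
- Follow-up height is fixed (SAP 9.5).
- Subjects are aged 6 to 18 with monthly visits for a year (SAP 3.1 and 3.3).

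**Inputs assumed**
- Starting height, starting weight, growth and weight gain, because the documents give none of them.

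**Algebra.** Let w0 and h0 be starting weight and height, and w1 and h1 the follow-up values. I take the fixed height to equal the starting height.
- SAP rule: change = (w1 - w0) / h0^2. As a percentage this is (w1 - w0) / w0, the percent change in weight.
- Visit height: change = w1/h1^2 - w0/h0^2.
- Overstatement of follow-up BMI: (h1/h0)^2 - 1, which is positive whenever h1 > h0.
- The SAP rule shows a rise while true BMI falls whenever 1 < w1/w0 < (h1/h0)^2.

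**Overstatement, ((h+g)/h)^2 - 1**

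| Starting height h | Growth g | Overstatement |
|---|---|---|
| any | 0 cm | 0% |
| 165 cm | 1 cm | 1.2% |
| 165 cm | 3 cm | 3.7% |
| 140 cm | 1 cm | 1.4% |
| 140 cm | 2 cm | 2.9% |
| 140 cm | 4 cm | 5.8% |
| 140 cm | 6 cm | 8.8% |
| 120 cm | 6 cm | 10.25% |

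**Sign reversal in one child.** Start at 140 cm with BMI 18, so w0 = 18 x 1.40^2 = 35.28 kg. The child grows 6 cm and gains 2 kg.
- Visit height: 37.28 / 1.46^2 = 17.49, change -0.51.
- SAP rule: 37.28 / 1.40^2 = 19.02, change +1.02.
- Percent changes: weight 2/35.28 = 5.67%; SAP-rule BMI 1.02/18 = 5.67%.

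For this child the sign is wrong for any gain below 35.28 x (((140+g)/140)^2 - 1), which is 1.02, 2.04 and 3.09 kg for g = 2, 4 and 6 cm.

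**Other assumed children**

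| Start | Growth, gain | SAP rule (kg/m2) | Visit height (kg/m2) |
|---|---|---|---|
| 130 cm, 28 kg | 6 cm, 2 kg | +1.18 | -0.35 |
| 145 cm, 38 kg | 6 cm, 5 kg | +2.38 | +0.79 |
| 160 cm, 52 kg | 4 cm, 2 kg | +0.78 | -0.24 |
| 172 cm, 65 kg | 0 cm, 2 kg | +0.68 | +0.68 |

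**Group mean when true BMI stays at 18.** If a fraction f of subjects start at 140 cm and grow g, and the rest do not grow, the spurious mean rise is f x 18 x (((140+g)/140)^2 - 1).

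| Fraction still growing | g = 4 cm (kg/m2) | g = 6 cm (kg/m2) |
|---|---|---|
| 0% | 0 | 0 |
| 25% | 0.26 | 0.39 |
| 50% | 0.52 | 0.79 |
| 75% | 0.78 | 1.18 |
| 100% | 1.04 | 1.58 |

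**The case against.** The strongest reply is that the two height sentences are leftovers. Height z-scores by visit cannot be produced from one baseline height, so the programmers may already use visit height, in which case no table is biased. That is plausible, and the documents cannot settle it. The bias is therefore a consequence of the rule as written, not a finding about the output. It is not a reason to leave the rule, because the SAP is the specification to which the table is programmed and checked.

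A second reply is that the exposure is limited. BMI is descriptive, is not a named endpoint, and drives no test, threshold or adverse event count. The weight summaries and the weight and height z-scores are unaffected by the BMI rule. This stands and limits the severity. The BMI z-scores are only a partial safeguard, since their height input is not stated.

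Third, the BMI table is not a literal copy of the weight table. The identity holds within a child for percent change, whereas the planned change is absolute and each child has a different height. That is correct, but it does not reduce the bias.

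Fourth, the size is assumed throughout. Bias is smaller at early visits and zero in adolescents who have stopped growing, and the worked cases show sign reversal for individuals, not for a group mean. All of this stands. The direction does not depend on those assumptions.

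Finally, the case report form is not available, and remote visits may lack a height. The availability of visit heights is inferred from the protocol.

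**Conclusion.** The concern holds. SAP 9.5 conflicts with the protocol's collection of height and with its own z-score analyses. Followed as written, it overstates follow-up BMI by (h1/h0)^2 - 1 in every child who grows. Over the assumed growth of 0 to 6 cm this is 0% to about 10%. Where true BMI is constant at 18, the spurious mean rise ranges from 0 to 1.58 kg/m2, depending on how many subjects are still growing and by how much. Individual changes can have the wrong sign. The direction is certain for any growing child; the size rests on assumed heights, weights and growth. The error is confined to descriptive safety output, plus the BMI z-scores if they use the same height, and it should be corrected.

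**What to change.** Replace the two height sentences in SAP 9.5 so that they say the following:
- Height is measured at Baseline and at each clinic visit, and is summarised by visit with change from baseline.
- BMI, height z-score and BMI z-score at a visit use the height measured at that visit, and are missing if height was not measured then.
- The reference to screening height is removed, and Baseline BMI uses the Baseline height.

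Record the correction in SAP 10 with the other changes made after database lock.

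The cost is two sentences, height rows in the vital signs summary, and a rerun of the BMI derivation. No new data are needed if heights were collected as the protocol requires. The downside is missing BMI at remote visits without a measured height. Reporting n at each visit, already part of the SAP 6.1 summary set, shows how much is lost.

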9.6. ECG

The following ECG data will be collected at Baseline, Months 1, 3, 6, 9 and 12:

- PR interval (msec)
- QRS interval (msec)
- QT interval
- QTc interval (msec)
- Overall ECG result (Normal; Abnormal, Not Clinically Significant; Abnormal, Clinically Significant).

An ECG is optional at unscheduled visits, per the investigator's discretion.

The actual ECG results along with change from baseline will be summarized at each visit. Shift (<=450, >450 to <= 480, > 480 to <= 500, >500) from baseline in QTc interval will be summarized by visit. ECG outliers for QTc interval (change from baseline>30 to <=60, >60), PR interval (>25% increase change from baseline,>200, >25% increase change from baseline and PR>200) and QRS interval (>25% increase change from baseline,>200, >25% increase change from baseline and QRS>200) will be summarized by visit and overall. All ECG data will be presented in a listing.

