2. SYNOPSIS

Name of Sponsor/Company:

Emalex Biosciences, Inc.

Name of Investigational Product:

Ecopipam Tablets

Protocol Number: EBS-101-OL-001

Title of Study:

A Multicenter, Open-Label, Extension Study Intended to Evaluate the Long-term Safety of Ecopipam Tablets in Children and Adolescent Subjects with Tourette's Syndrome

Study center(s): Approximately 60 sites in US, Canada and EU

Principal Investigator: TBD

Investigators: TBD

Studied period (years):

Estimated date first patient enrolled: 3Q2019

Estimated date last patient completed: 2Q2023, or until NDA

approval or until development is discontinued by the

Sponsor, whichever is sooner

Phase of development:

2b

Objectives:

The primary objective of this study is to evaluate the long-term safety and tolerability of ecopipam tablets in pediatric subjects (aged ≥ 6 to ≤ 18 years at Baseline) with Tourette's Syndrome (TS) that were previously enrolled in the EBS-101-CL-001 study (Phase 2b) and completed the Phase 2b study. The secondary objective is to evaluate the durability of effect of ecopipam in pediatric subjects (aged ≥ 6 to ≤ 18 years at Baseline) with TS.

Methodology:

This is an international, multicenter, open-label, long-term extension study evaluating the safety of ecopipam tablets for the treatment of children and adolescent subjects with TS. Subjects who completed the Phase 2b, randomized double-blind efficacy and safety study (EBS-101-CL-001) and who continue to meet the inclusion/exclusion criteria for this study will be eligible to participate in this study. All subjects will be titrated to a target dose of 2 mg/kg/day as subjects participating from previous studies will be tapered off of study medication to maintain the blind. Subjects will complete study visits every month for 1 year. Follow Up visits will be conducted 7 and 14 days after the last dose of study medication and a Follow Up phone call will be conducted 30 days after the last dose of study medication. Study Visits may be completed in locations other than clinic and/or safety and efficacy assessments required at these visits will be made available for remote administration due to restrictions as a consequence of the COVID-19 pandemic or other qualifying event.

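### No count is planned of distinct children whose QTc ever exceeded 450, 480 or 500 msec after Baseline; secondarily, the QTc correction formula is not stated

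*SAP*

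**What the plan says.** SAP 9.6 sets the schedule: "The following ECG data will be collected at Baseline, Months 1, 3, 6, 9 and 12". That is one Baseline and five post-baseline ECGs. The fields are PR, QRS, QT, QTc and an overall interpretation. No correction formula is named there or anywhere else in the protocol or SAP, and neither RR nor ECG heart rate is among the fields. Values are used as recorded: "The actual ECG results along with change from baseline will be summarized at each visit".

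Two QTc tables follow.

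- Table 14.3.4.7a: "Shift (<=450, >450 to <= 480, > 480 to <= 500, >500) from baseline in QTc interval will be summarized by visit".
- Table 14.3.4.7b: "ECG outliers for QTc interval (change from baseline>30 to <=60, >60", with PR and QRS limits that include an absolute value above 200. This table is given both by visit and overall.

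SAP section 10 lists both among the items added after database lock ("A summary of shifts from baseline in 12-lead ECG QTc will be provided in Table 14.3.4.7a"), and the index of tables in SAP section 14 places them under a post-hoc heading. Heart rate is handled separately in SAP 9.5, as a vital sign with its own outlier limits: ">25% increase change from baseline, >100, >25% increase change from baseline and >100 will be summarized by visit and overall".

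Two general rules bear on which ECGs reach a table. SAP 6.1 leaves unscheduled visits out of summaries and puts them in listings. SAP 6.4 applies visit windows to ECG data and keeps only the record closest to the target day.

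**The concern.** Long-term safety is the primary objective and there is no concurrent control. The natural QTc question is how many children went above a given limit at any time on treatment. The plan answers the equivalent question for absolute PR, absolute QRS and QTc change, but not for absolute QTc. A series of by-visit counts cannot be turned into a count of children without knowing whether the same children recur, and a child's highest value may not be in any by-visit table.

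The secondary issue is what the 450 limit measures. Bazett and Fridericia values diverge as heart rate moves away from 60 bpm. The protocol synopsis plans "Approximately 60 sites in US, Canada and EU", and nothing in the plan fixes one formula across sites or between a child's Baseline and later ECGs. The footnote to Protocol Table 2 also allows Baseline measurements to come from the parent study's Day 14 Follow Up Visit. Fixed limits are therefore applied to a variable whose definition is not stated.

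**Working it through.** The plan states no figure of its own to reproduce here.

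**1. Which QTc summaries are planned**

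| Quantity | By visit | Overall |
|---|---|---|
| PR, QRS above an absolute limit | yes | yes |
| QTc change >30 to ≤60, >60 | yes | yes |
| QTc >450, >480, >500 | yes (shift) | no |

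I read overall as any post-baseline visit; SAP 9.6 does not define it.

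**2. What by-visit counts can say**

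Input: five post-baseline ECGs (SAP 9.6). If n1 to n5 children exceed a limit at the five visits, the number of distinct children lies between max(n1…n5) and n1+…+n5. With k at every visit the range is k to 5k. Per-visit rates below are assumed for illustration; the independent case is 1 − (1 − p)^5.

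- p = 1%: ever-exceeded share from 1% to 5%; 1 − 0.99^5 = 4.9% if visits are independent.
- p = 2%: from 2% to 10%; 1 − 0.98^5 = 9.6% if independent.

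**3. ECGs that may reach no table**

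SAP 9.6 allows optional ECGs at unscheduled visits. Under SAP 6.1 these are only listed. Under SAP 6.4, if two ECGs fall in one window, the one nearer the target day is used whichever is higher; the higher value is preferred only in a tie. SAP 6.1 also says by-visit summaries use the nominal visit, so it is not clear whether windowing can bring an unscheduled ECG into a table. On either rule a child's maximum can be left out.

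**4. Heart rate and the formula (conditional)**

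QTcB = QT/RR^(1/2) and QTcF = QT/RR^(1/3), so QTcB = QTcF × (HR/60)^(1/6). Hold QTcF constant, vary only heart rate and suppose Bazett is recorded. The QTcF and rate values are assumptions.

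- QTcF 420, 75 to 95 bpm: 420 × 1.25^(1/6) = 435.9; 420 × (95/60)^(1/6) = 453.4. This crosses 450 with a change of 17.5 msec.
- QTcF 420, 80 to 100 bpm: 440.6 to 457.3, which also crosses 450.
- Rate at which Bazett reads 450: 60 × (450/QTcF)^6 = 90.8 bpm at QTcF 420, 104.9 at 410, 121.6 at 400.
- Rate ratio for +30 msec: ((QTcB + 30)/QTcB)^6. From QTcB 400 it is 1.54 (60 to 92.6 bpm); from 430.9 it is 1.50 (70 to 104.8 bpm).
- Rate at which Bazett reads 480: 60 × (480/QTcF)^6 = 133.7 bpm at QTcF 420, 154.5 at 410, 179.2 at 400.

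If instead the formula differed between a child's two ECGs at a constant rate, a 30-msec gap at QTcF 400 would arise at 60 × (430/400)^6 = 92.6 bpm.

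**5. Whether the vital-sign pulse can stand in for ECG rate**

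QTcF = QT × (HR/60)^(1/3). With a true QTcF of 400 at a tracing rate of 80 bpm, QT = 400 × (60/80)^(1/3) = 363.4. Using a pulse of 90 gives 416 (+16); using 100 gives 431 (+31). The substitution can itself cross the 30-msec limit.

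**The case against.** The strongest reply is that little is lost. All ECG data are listed, so distinct children can be counted by hand. By-visit summaries show the maximum, so a reader sees whether anyone exceeded 480 or 500 at each visit. If no visit, or only one, has exceedances, the distinct count from the summarised ECGs is already exact. QTc change above 30 and 60 msec does have an overall row. The protocol promises only descriptive by-visit ECG summaries, QTc is not an adverse event of special interest, and the earlier experience cited in the protocol reports no clinically significant ECG findings. All of this stands. It limits the weight of the point, but it does not supply the row that PR and QRS already have.

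On the formula, the documents do not say that Bazett was used or that sites differed, and they give no heart-rate data for these children. If every recorded QTc is Fridericia, the drift in step 4 is zero. The formula may also be recorded in ECG or data-entry instructions outside these documents. Nor is Fridericia free of rate dependence: if the Bazett value were the constant one, at 400 to 420, a fall from 100 to 65 bpm would raise the Fridericia value by 27 to 29 msec. The gain from one formula is consistency and a stated definition.

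A reader might also infer that a common QTc cannot be recovered. That goes too far. QT and QTc are both recorded, so once the source formula is known RR follows: (QT/QTc)^2 for Bazett, (QT/QTc)^3 for Fridericia.

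**Conclusion.** The main point holds without any assumption about the formula: no count of distinct children ever above 450, 480 or 500 msec is planned, and by-visit counts leave up to a fivefold range when exceedances occur at every visit. The ambiguity bites only if exceedances occur at more than one visit, or on ECGs that the tables leave out.

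The secondary point is conditional on Bazett or mixed formulas. It then bears mainly on the 450 boundary, where a 20-bpm rise can suffice for a child near the limit. Rate alone reaches 30 msec only with a rise of about 50%, and 480 only at about 134 bpm or more for QTcF up to 420.

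Two stronger readings are not supported. One is that exceedances above 480 or 500 would be invisible: the listing and the by-visit table show them. The other is that the QTc outliers in this trial are produced by heart rate or by differing machines: nothing in the documents establishes which formula was used. This is a cheap improvement to a safety table, not a flaw that invalidates the ECG analysis.

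**What to change.** 1. In SAP 9.6 and Table 14.3.4.7b, add any-post-baseline rows for QTc >450, >480 and >500 msec. Count each child once by maximum post-baseline QTc, include unscheduled ECGs and ECGs not selected by windowing, and use as denominator the children at or below that limit at Baseline. The cost is three rows and a footnote. Both QTc tables are already post-hoc additions, so no prespecified analysis is disturbed.

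2. State the correction formula. Use one formula (for example QTcF) for every ECG including Baseline, in Tables 14.3.4.3.1, 14.3.4.7a and 14.3.4.7b. Take RR from the same tracing, or back-calculate it from recorded QT and QTc where the source formula is known. Keep the collected QTc in the listing. Do not substitute the vital-sign pulse, for the reason in step 5.

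The second change may cost more than wording: the source formula or ECG rate may have to be retrieved from sites after database lock. Where it cannot be, report the collected QTc and state that its formula is unknown. The first change does not depend on the second and can be made at once.

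### SAP 9.6 gives QRS the same 200 msec outlier limit as PR without justification, so two of the three QRS rows are expected to be empty and only the relative-change row does any work

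*SAP*

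**What the plan says.** SAP 9.6 lists PR and QRS among the ECG intervals, both in msec. The outlier criteria for PR are "PR interval (>25% increase change from baseline,>200, >25% increase change from baseline and PR>200", and those for QRS are "QRS interval (>25% increase change from baseline,>200, >25% increase change from baseline and QRS>200". Apart from the interval's name they are the same, including the number 200; the combined criterion, for instance, ends "25% increase change from baseline and PR>200" for PR and "25% increase change from baseline and QRS>200" for QRS. The outliers are to be counted by visit and overall in Table 14.3.4.7b.

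Other ECG displays in the same section also bear on QRS. "The actual ECG results along with change from baseline will be summarized at each visit" (Table 14.3.4.3.1). The investigator's overall result (normal, or abnormal with or without clinical significance) has its own table (14.3.4.3.2). All ECG data are listed (Listing 16.2.8.3). A shift table against fixed bands is planned for QTc only: the shift "from baseline in QTc interval will be summarized by visit" (Table 14.3.4.7a).

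SAP section 10 places the outlier table among the additions made after database lock, and the index of tables in section 14 puts it under a post-hoc heading. Neither document gives a QRS reference range, a QRS-specific limit or a reason for choosing 200.

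**The concern.** PR and QRS are different intervals, yet they share one absolute limit. The three-row format pairs a relative change with a limit suited to the parameter. Heart rate in SAP 9.5 has its own limits (50 and 100), and QTc has its own bands. If the limit lies far above the values that QRS takes, the absolute row cannot fill, and the combined row repeats it. The QRS part of the table then rests on relative change alone.

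Long-term safety is the primary objective of this paediatric study. What is at stake is modest but real. Two rows of zeros could be read as reassurance about QRS when they mainly reflect where the limit was set, and a subject who drifts across a clinically relevant QRS limit by a modest percentage would be counted nowhere.

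**Working it through.** There is no sample size, power or error rate to reproduce. The check concerns the logic of the three criteria.

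**Inputs.** From SAP 9.6: relative criterion, rise above 25%; absolute criterion, above 200; combined criterion, both; unit msec. By assumption: baseline QRS of 60 to 120 msec. Protocol 8.2, exclusion 4, removes subjects whose baseline ECG abnormality is judged clinically significant. That supports the assumption but supplies no number.

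**1. When the combined row repeats the absolute row.** Let b be the baseline and q the on-treatment value. If q > 200 and b ≤ 200/1.25 = 160, then q/b > 200/160 = 1.25, so the rise already exceeds 25%. Listing integer pairs with b from 60 to 160 and q from 201 to 300 gives no pair that meets the absolute criterion but not the combined one. The first such pair is b = 161, q = 201, because 1.25 × 161 = 201.25, which is above 201.

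**2. How far QRS must rise to pass 200.** Required rise = 200/b − 1; the relative row triggers above 1.25b.

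| Assumed baseline (msec) | Rise needed to pass 200 | Relative row triggers above (msec) |
|---|---|---|
| 60 | 233% | 75 |
| 80 | 150% | 100 |
| 100 | 100% | 125 |
| 120 | 67% | 150 |

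**3. How likely values above 200 are without a marked shift.** Under an assumed normal distribution with mean 100 and SD 15, z = (200 − 100)/15 = 6.67 and P(QRS > 200) is about 1.3 × 10⁻¹¹. Under a deliberately wide assumption of mean 110 and SD 20, z = 4.5 and the probability is about 3.4 × 10⁻⁶. With that wide assumption, P(baseline > 160) is about 0.006, so the condition for duplication in step 1 would still cover more than 99% of subjects.

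**4. What the three rows miss.** Take a lower limit L. A subject with baseline between L/1.25 and L can cross L with a rise of 25% or less. The values of L below are for illustration only; the documents give none.

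| Assumed L (msec) | Baselines that can cross L unflagged (msec) |
|---|---|
| 100 | 80 to 100 |
| 110 | 88 to 110 |
| 120 | 96 to 120 |

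For example, a subject going from 100 to 124 msec rises by 24%. That is not above 25%, not above 200 and not both, so no row counts the subject, although the value has passed 110 and 120.

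**5. What a lower limit would restore.** With limit L, the absolute and combined rows can differ for baselines above L/1.25, that is above 80, 88 or 96 msec for the three illustrative limits, and no longer only above 160.

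**The case against.** The strongest reply is that little is lost. The relative row stands alone in the same table and triggers above 75 to 150 msec over the assumed baselines, so a marked QRS prolongation is counted by visit and overall. Means, changes from baseline, the overall ECG interpretation and a full listing remain. Protocol 12.2.1 also makes an ECG abnormality an adverse event when the investigator judges it clinically significant. All of this stands, and it limits the point to two rows of one descriptive table. It does not close the gap in step 4, because none of those displays counts QRS values against a limit.

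A reader might infer more than the documents support:

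- **That the two rows are empty by construction.** Only their equality follows from the definition, and only for baselines up to 160 msec. Emptiness depends on the assumed baseline range.
- **That the table will report no QRS outliers.** The relative row can still report them.
- **That the rule is sound for PR and fails only for QRS.** The 160 msec threshold for duplication applies equally to PR, and the documents give no PR values. Heart rate in SAP 9.5 behaves in the same way: for a baseline up to 100/1.25 = 80, exceeding 100 already implies a rise above 25%. Overlap belongs to the format; what is specific to QRS is how far 200 lies from the assumed baseline.
- **That 200 was copied from PR by mistake.** The text shows only that the two numbers are equal and unexplained.

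A further objection concerns timing: a new limit chosen after database lock could be steered by the data. That is fair and shapes the remedy.

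**Conclusion.** The point holds in a limited form. SAP 9.6 applies 200 msec to QRS as it does to PR, with no justification for QRS. For baselines up to 160 msec the absolute and combined QRS rows are identical; this is arithmetic and needs no assumption beyond that bound. Both rows are expected to be empty if baseline QRS lies at about 60 to 120 msec, since passing 200 would then need a rise of more than 67% to 233%. This part rests on a declared assumption, but the conclusion is the same across that range.

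In practice one of the three QRS rows does the work, and it is purely relative. Crossing a lower limit with a rise of 25% or less goes uncounted. The consequence is minor: the table is descriptive and post hoc, and no inference depends on it.

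**What to change.** Replace 200 in both the absolute and the combined QRS criteria of SAP 9.6 with a QRS-specific limit suited to this age range, with its source stated, or justify 200 for QRS. The sponsor's ECG reviewer should set the limit without reference to the observed QRS data. No number is proposed here, because the documents offer no basis for one and the illustrative limits above overlap the assumed baselines.

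Because of that overlap, count subjects who are already above the limit at baseline separately; otherwise they would appear as absolute outliers without any change. Record the change in SAP section 10 as a post-hoc revision.

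The cost is one number in the SAP and one rerun of Table 14.3.4.7b on data already collected. Some QRS outliers may then appear where the present criteria would show none.

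If 200 is kept, a footnote should say that the two limit-based QRS rows coincide for baselines up to 160 msec and that zeros there are not evidence against smaller prolongation.
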